2. Protocol Registration:

Protocol will be registered on clinicaltrials.org

3. Protocol version: 1

4. Funding:

The proposed clinical trial is self-funded.

5. Roles and responsibilities:

[name]: Department of Pediatric Dentistry and Dental Public Health Department, Faculty of Dentistry, Cairo University.

- Performs the clinical trial.
- Ensures participants' adherence throughout the trial.
- Collects the baseline data, results, interpretation and conclusions.
- Provide proper ancillary and post-trial care for all participants.
- Write the thesis.

Main supervisor & scientific advisor:

[name]. [name]: Professor of Pediatric Dentistry and Dental Public Health Department, Faculty of Dentistry, Cairo University.

- Monitors the whole process from the beginning of the trial and data collection.
- Assesses the final results and data collected from the study.
- Revises the thesis.

Co-supervisor:

[name]: Lecturer of Pediatric Dentistry and Dental Public Health Department, Faculty of Dentistry, Cairo University.

- Helps developing the protocol.
- Generates a random sequence to enroll the participants and undergoes proper allocation concealment, implementation, and access to the final data.
- Monitors the process of data collection and checks if there are any harms to the participants.
- Revises and helps in writing the thesis.

II. Introduction:

A) Background and rationale:

6.a. Research question:

In a child with cariously exposed vital primary molars, would it be better to use Collagen based pulpotomy or Biodentine based pulpotomy in terms of clinical and radiographic success of the pulpotomy procedure?

6.a. Statement of the problem:

Pulpotomy of vital primary molars is indicated when caries removal results in pulp exposure. Treatment approaches consist of devitalization using formocresol, preservation using ferric sulfate and regeneration of the remaining pulp tissue using mineral trioxide aggregate and recently Biodentine have been utilized. The ideal pulpotomy medicament would be biocompatible and bactericidal, in addition, to promoting the healing of the root pulp and be compatible with the physiological process of root resorption. (1)

Searching for more pulpotomy agents, Collagen, a protein that's present abundantly in humans, is an important component of connective tissues and performs multiple functions including wound healing.

Enamel and dentin contain Collagen as one of the components in their organic ground matrix.

Collagen has been used widely in dentistry in periodontal and implant therapy as scaffold for preventing the migration of epithelia cells and encouraging wound repopulation by cells with high regenerative potential. (2)

The Collagen available for dental implication is already sterilized and also reinforced with antibiotic particles to efficiently aid in regeneration and repair without any contaminations. The collagen particles can be sterilized by various methods like irradiation, dry heat, and ethylene oxide, among which irradiation is the most frequently used method as it does not affect the structural stability. (3)

6.a. Rationale for carrying out the trial:

There is insufficient evidence on the outcome of pulpotomies in carious exposed young permanent molars with newer biomaterials.

Searching for new and alternative pulpotomy materials with higher clinical efficacy and minimum secondary (adverse) effects.

Dental caries has a higher prevalence rate in children, especially in mixed dentition period due to their diet pattern change or lack in maintaining proper oral hygiene. In the case of dental caries with pulpal involvement, preserving the natural tooth by pulp therapy until its time of exfoliation is a vital aim in pediatric dental management, as they are said to be the best space maintainers. Among different pulp therapy strategies, vital pulpotomy is the topic of interest in this study.

By definition, a pulpotomy is defined as partial removal of the pulp (coronal portion) and leaving radicular pulp intact, after establishing effective hemostasis, restoration with biocompatible materials.(4)

Benefits for the practitioner:

- providing new and alternative treatment options.
- Less technique sensitive.
- Easier application of the material during pulpotomy that eliminates hand mixing (auto-mix).
- Improved chairside delivery owing to its better consistency and adequate working time.

Benefits for the patient:

- A faster and easier process leading to a more efficient dental procedure which could develop better outcomes in terms of success.
- A more comfortable dental procedure to improve patient as well as parent satisfaction.

Benefits for community:

- Using alternative material that can be more cost effective, affordable treatment for children thus saving more primary teeth.
- To boost overall oral health.

6.b. Review of literature:

Pulpotomy is considered the gold standard procedure for treating cariously exposed pulps in asymptomatic primary teeth. Which is based on the healing ability of the radicular pulp tissue following amputation of the infected coronal pulp. (5)

Mineral trioxide aggregate (MTA) has been recommended as the gold standard for vital pulp therapy; however, it has some disadvantages, such as long setting time, poor handling properties, high cost, and the potential for tooth discoloration. Biodentine (Septodont, Saint-Maur-des-Fossés, France), one of the new-generation, bioactive endodontic cements, has been claimed to have improved properties over MTA.

Biodentine presents high biocompatibility with the dental pulp, it has high antibacterial effects and antifungal activity, has a shorter setting time than MTA as a result of the calcium chloride in the liquid component of Biodentine. It also has higher flexural strength, compressive strength and modulus of elasticity than MTA. Consequently, Biodentine can be used as a pulp dressing as well as a base material. (6)

Quest is on for newer pulpal medicaments that are biocompatible and capable of healing the dental pulp by producing reparative dentin and/or dentinal bridge in response to various stimuli and surgical exposure.

Collagen has a proven rate of success in the field of dentistry as guided tissue regeneration, root conditioning, hemostatic, and wound dressing agent. It has inherent properties like low immune response and toxicity, ability to promote cellular growth and attachment, homeostasis, and added advantage of antibiotic incorporation. (7)

7. Objectives:

Aim of the study

To assess clinical and radiographic success after collagen based pulpotomy versus Biodentine pulpotomy in children with cariously exposed vital primary molars.

Hypothesis:

Null hypothesis: No added benefits will be gained from the collagen based pulpotomy clinically and radiographically.

PICO approach:

P: Population: Children 4-7 years with carious vital primary molars.

I: Intervention: Sterile medicated Collagen particles.

C: Control: Biodentine.

O: Outcome:

Outcome		Method of measurement	Unit
1ry outcome: Clinical success	1- Absence of internal root resorption	Periapical X-ray (parallel technique)	Binary
2ry outcome:	1- Absence of pain	Questioning the patient	Binary
	2- Absence of swelling	Visually by intraoral and extraoral examination	Binary
	3- Time elapsed till final restoration performed	Stopwatch	Continuous outcome measured in minutes

(S) Study design: Randomized controlled.

(T) Time of follow up:6 months.

8. Trial design:

Randomized controlled trial (R.C.T).

III. Methods

A) Participants, interventions & outcomes:

9. Study settings:

This study will be carried out on patients attending the out-patient clinic in Pediatric Dentistry and Dental Public Health Department-faculty of Dentistry, Cairo University, Egypt.

The procedure will be carried out by postgraduate student [name], B.D.S(2014)-Pharos University in Alexandria (PUA) and without an assistant.

10. Eligibility criteria:

Inclusion criteria:

- Children:

- 1- Aged 4 to 7, in good general health and medically free.
- 2- Cooperative patients who will comply to follow ups.
- 3- Parents provided with written informed consent.

- Teeth:

- 1- Bilaterally Carious vital primary molars with reversible pulpitis.
- 2- Restorable teeth with no more than 1/3 of root resorption.

Exclusion criteria:

- Children:

- 1- Children with medical, physical, or mental conditions.
- 2- Unable to attend follow up visits.

- Teeth:

- 1- Primary molars with any congenital anomalies.
- 2- Previously accessed teeth.
- 3- At operative procedure, haemorrhage control is unachievable after pulpotomy.

11. Interventions

The principal investigator will carry out all treatment procedures, using the split mouth technique, meaning that both groups (I & II) will be in the same patient.

For both interventions:

1. Informed consent from participating parents.
2. Baseline records photographs, percussion test, periapical radiograph, and personal data collection (Appendix 1: Diagnostic chart).
3. Allocation (concealed by withdrawing a sealed opaque envelope containing eight times folded paper containing the type of dressing material that will be used then writing patient name and ID on it and will be opened after performing the access cavity).
4. Diagnostic chart with personal, medical, and dental history will be filled (Appendix 1: Diagnostic chart).
5. Clinical examination will be performed to assess the clinical inclusion criteria. (Pulpal and periapical diagnosis is established after clinical examination).
6. Preoperative and Postoperative photographs will be taken.
7. The radiographic examination will be performed by taking periapical x-ray using (parallel technique) through machine to assess the inclusion criteria. The preoperative radiograph will serve as a reference for the follow-up radiographs. Standardization of the technique to avoid any distortion in the vertical dimension and to provide reproducible images using x-ray holding device.
8. Preoperative and postoperative radiograph will be taken by parallel technique using XCP film holder (Super Bite, Hawe Neos Dental SA, Switzerland).
9. Administration of inferior alveolar nerve block (Septodont, Scandonest® 2% L Mepivacaine HCl. 2% and Levonordefrin 1:20,000 Injection, U.S.P.) at the side of the affected tooth.
10. Application of rubber dam for isolation, then a standardized pulpotomy procedure will be performed using a large sterile round end bur in a high-speed handpiece with copious irrigation, a sharp spoon excavator will remove pulpal tissues to the orifice level. Hemostasis will be achieved by the application of a wet cotton pellet to achieve complete hemostasis.
11. Children will then be allocated into either one of the groups alternatively depending on the pulpotomy medicament used as follows:
Group I (Experimental group) collagen based pulpotomy.
Group II (Control group) Biodentine pulpotomy.

Group I (Experimental group) collagen based Pulpotomy:

1. Collagen based pulpotomy will be applied (sterile medicated collagen particles, Biofil-AB, Eucare Pharmaceuticals Pvt. Ltd, Chennai, India) according to the manufacturer's instructions and gently placed over the pulp stumps to a thickness of 2 mm.

Group II (Control group) Biodentine pulpotomy:

1. Biodentine (Septodont, Saint-Maur-des-Fossés, France) will be applied according to the manufacturer's instructions and placed over the radicular pulp with the help of a suitable sterile amalgam carrier. Gentle condensation of the mix will be done in the pulp chamber with a moistened cotton pellet.

12. For both groups;

The rest of the pulp chamber will be filled with glass ionomer cement.

Tooth will then be restored with stainless steel crown (3M ESPE, St Paul, MN, U.S.A.).

12. Outcomes:

Primary outcome:

Absence of periapical radiolucency and internal/ external root resorption (Binary outcome detected with periapical x-ray by Parallel technique using XCP film holder (Super Bite, Hawe Neos DentalSA, Switzerland).

Secondary outcome:

1- Survival rate (absence of any complication or complementary treatment) in terms of:

1-Absence of spontaneous pain. (Binary outcome measured with direct questioning to the patient).

2-Absence of swelling. (Binary outcome measured visually by intraoral/extraoral examination).

2- Time elapsed till final restoration performed.

13. Participant timeline:

Patients will be diagnosed to determine whether they are eligible for the inclusion criteria of this study or not.

Eligible patients will then start their treatment on the same visit.

	STUDY PERIOD					
	Enrolment	Allocation	Treatment visit	Post-treatment	Close-out	
TIMEPOINT	-t1	0	0	T1 (3m)	T2 (6m)	
ENROLMENT:						
Eligibility screen and patient selection	X					
Informed consent from participating pts	X					
Allocation (concealed in closed white envelop)	X					
INTERVENTIONS:						
The pulpotomy procedure (gaining access to the pulp)		X				
Allocation of the patient to one of the treatments groups (open the closed white envelope)		X				
Application of pulp dressing material (collagen and Biodentine)			X			
Final restoration			X			
ASSESSMENTS:						
baseline variables	1- photographs	X		X	X	X
	2- percussion test	X		X	X	X

	3- preoperative periapical radiograph	X				
	4- personal data	X				
outcome variables	Calculation of time-elapsed till final restoration			X		
	Questioning the patient about the absence of spontaneous pain	X			X	X
	Visual examination of patient to check the absence of sinus or Swelling	X			X	X
	Periapical radiograph to check the absence of periapical radiolucency, internal/ external root resorption	X		X	X	X

14. Sample size:

Sample size will be calculated.

15. Recruitment:

Patients attending the out-patient clinic in the pediatric dentistry department- Cairo University, having bilateral carious lower molars will be carefully assessed for eligibility to participate in our study by one of the main investigators [name], then a full explanation of the nature of our experiment and the importance of maintaining this primary tooth and restoring it for proper functions and the drawbacks of extracting it. Full mouth treatment will be offered for them.

B) Assignment of interventions:

16. Allocation:

16a. Random sequence generation (Randomization):

Teeth that will be included in the current trial will be randomly assigned one of the experimental groups using closed white envelopes (simple randomization 1:1 ratio).

a) Sequence generation:

By shuffling the envelopes then selecting envelop for each patient upon their enrolment.

b) Allocation Concealment:

Using 8-time folded paper on which dressing material was written contained in the closed white envelope.

c) Implementation:

When a patient agrees to participate in the trial, an envelope will be drawn by one of the residents present at the clinic and name, telephone number and patient's ID will be written on it. Those selected envelopes will be opened at treatment visit after performing pulpotomy to choose which material should be used.

Randomization and allocation concealment will be performed by the co-supervisor to avoid selection bias.

17. Blinding:

The blinding is not possible (unfortunately) due to the nature of the trial.

Trial participants, outcome assessors and statistician will be blinded.

C)Data collection, management, and analysis:

18. Data collection methods

Baseline data collection

Plans for assessment and collection of outcomes will be at 3 and 6 months clinically (using visual examination, palpation, and percussion test with back of the mirror) and 0 and 6 months radiographically (using periapical radiograph) and will be done by two blinded assessors independently, and differences will be solved by consensus. To promote data quality, duplicate measurements by the same examiner (intra-examiner agreement) and training of assessors (inter-examiner agreement) will be done.

19. Data management:

Data will be recorded on a diagnostic chart for each patient separately and will be stored with follow up periapical radiographs.

20. Statistical methods:

Clinical and radiographic outcomes will be submitted for statistical analysis by the Statistical Package for Social Science (SPSS) program windows version 13. Results will be calculated using risk reduction (R.R.).

D) Data monitoring:

21. Monitoring

The study work results will be monitored regularly by the supervisors who will have full access to these interim results make the final decision to terminate the trial.

22. Harms

- **Bur breakage:** the bur will be replaced by a new one and treatment will be proceeded.
- **Perforation of pulpal wall or floor:** The tooth condition and size of perforation will be assessed whether the treatment will be to repair the perforation and treatment will be proceeded (the tooth will be removed from the trial) or the tooth will be extracted, and space maintainer will be performed
- **No reported hypersensitivity from both tested materials.**
- **Failure of pulpotomy procedure:** retreatment of the tooth through partial pulpectomy and tooth will be removed from the trial.

23. Auditing

The study supervisors will regularly assess the trial process and documents. They will be involved in participant enrolment, consent, eligibility and allocation to study groups, adherence to trial interventions and policies to protect participants, including reporting of complications and their treatments. Clinical procedures will be performed under their supervision.

IV. Ethics and dissemination

24. Research ethics approval:

This protocol, the template and specific informed consent forms (local language and English versions) will be reviewed, approved, and agreed upon by the (Research Ethics Committee) will review all the nature of interventions and will have the right to modify the study methods.

25. Protocol amendments:

The Ethics Committee will be notified of any administrative changes or modifications of the protocol. Any required changes during the trial period for the patient's own interest that might affect the conduct of the study, including changes of the study objectives, study design, patient population, sample sizes, intervention procedures will require a formal amendment to the protocol. Such amendment will be agreed upon by the Council of the Department of Pediatric Dentistry, Faculty of Dentistry, Cairo University.

26. Informed consent:

The investigator will discuss the trial with the legal guardian of each participating child:

- Verbal permission will be taken orally from participating child.
- Written informed consent will be taken from the legal guardian of each participating child willing to participate in the trial. The consent form will be written in Arabic.

27. Confidentiality:

All data, information, participant's personal information, family history, social and medical history will be stored in the files assigned to each patient with limited access to a minimum number of individuals necessary for quality control, audit, and analysis.

28. Declaration of interest:

This study is a part of a master's degree in Pediatric Dentistry, Faculty of Dentistry, Cairo University. No financial conflict of interests is confirmed. The study is self-funded by the principal investigator.

29. Access to data:

The investigator will be given access to data sets. All data sets will be password protected. To ensure confidentiality, data dispersed to project team members will be blinded of any identifying participant information.

30. post-trial care:

The investigator will offer full mouth treatment, post-operative care, and preventive measures to all participants.

31. Dissemination policy:

The Thesis defense will be done as the study is a part of the requirements for a master's degree in Pediatric Dentistry. Also, the results of the study will be published in Journals.

V. Appendices**Appendix 1: Chart filled for each patient in this trial:**

Patient name:

Patient ID:

Tested material:

Age:

sex:

Address:

Telephone:

Chief complain of the patient:

Pretreatment medications:

Participating tooth:

Date of material application:

Follow up		1ry outcomes assessment clinical assessment (survival rate)		2ry outcomes assessment Radiographic assessment			Final assessment “success or failure”
Time after	Date	1- Spontaneous pain	2- Swelling	3- Internal root resorption	4 - External root resorption	5- Periapical radiolucency	
3m	/ /20						
6m	/ /20						

VI. References:

- 1- izGuven SD. *Success Rates of Pulpotomies in Primary Molars Using Calcium SilicateBased Materials: A Randomized Control Trial. Biomed Res Int.* 2017;2017:7.
- 3- *Use of collagen as a biomaterial: An update - researchgate. (n.d.). Retrieved March 6, 2022, from* https://www.researchgate.net/publication/258204888_Use_of_collagen_as_a_biomaterial_An_update
- 5- J. Camilleri. “Hydration characteristics of biodentine and theracal used as pulp capping materials.” *Dent Mater.* 2014;30:709–715.

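### The protocol opens the allocation envelope at two different operative moments; under one of them the haemorrhage exclusion is decided with the material already known

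*Protocol*

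**What the plan says.** Four places in the protocol fix when the allocation is revealed.

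- Section 11, step 3: the envelope "will be opened after performing the access cavity".
- Section 11, step 11, which follows pulp removal and haemostasis in step 10: "Children will then be allocated into either one of the groups alternatively depending on the pulpotomy medicament used as follows". Only its position in the sequence matters here.
- Section 13, timeline: one row reads "The pulpotomy procedure (gaining access to the pulp" and the next "Allocation of the patient to one of the treatments groups (open the closed white envelope". Both are marked in the allocation column, and haemostasis has no row.
- Section 16(c): "Those selected envelopes will be opened at treatment visit after performing pulpotomy to choose which material should be used".

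Two further passages matter. Section 10 excludes a tooth on this ground: "At operative procedure, haemorrhage control is unachievable after pulpotomy". Section 11, step 10 describes the haemostasis step: "Hemostasis will be achieved by the application of a wet cotton pellet to achieve complete hemostasis". No time limit or number of attempts is given.

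On the operator, section 11 states: "The principal investigator will carry out all treatment procedures, using the split mouth technique". Section 17 lists participants, outcome assessors and the statistician as blinded, but not the operator.

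**The concern.** Step 3 and step 11 cannot both be followed, because the pulp removal and haemostasis of step 10 lie between the two moments. A tooth-level eligibility decision also falls in that interval. Since the operator is not blinded, not yet knowing the allocation is the only safeguard on that decision, and step 3 removes it.

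The risk is selection after randomisation. Poor haemostasis plausibly predicts pulpotomy failure. If borderline teeth are kept more readily for one material than for the other, the arms differ in prognosis for reasons unrelated to treatment. No bad faith is needed: section 6.b itself credits collagen with haemostatic properties, which could colour a close call. Once made, such exclusions cannot be undone in the analysis.

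**Working it through.** **Order of events under each text**

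| Text followed | Sequence | Material known at the haemorrhage exclusion? |
|---|---|---|
| Section 11, step 3 | access, envelope opened, pulp removal, haemostasis, exclusion decision | Yes |
| Section 11, steps 10 and 11 | access, pulp removal, haemostasis, allocation | No, for the first tooth treated |
| Section 16(c) | access, pulp removal, envelope opened; haemostasis not explicitly placed | Not settled by its own wording |
| Section 13, timeline | pulpotomy, glossed as access, then envelope opened; haemostasis not listed | Not settled |

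Section 16(c) and exclusion 3 both use the pulpotomy as their reference point, so 16(c) read in isolation does not say which comes first, the opening or the bleeding decision.

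**Size of a possible bias**

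The protocol has no figure to reproduce: it gives no failure rate, exclusion rate or sample size. All inputs below are assumptions.

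- Failure with good haemostasis: 5%.
- Failure with borderline haemostasis: 30%.
- Share of teeth that are borderline: h = 10%, with 5% and 20% as a range.
- Teeth are independent and the materials do not truly differ.
- One arm keeps all borderline teeth; the other drops a fraction d of them.

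Arm keeping all: 0.05(1 − h) + 0.30h = 0.05 + 0.25h.

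Arm dropping a fraction d: [0.05(1 − h) + 0.30h(1 − d)] / (1 − hd).

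For h = 0.10, the arm keeping all has 0.05 + 0.025 = 7.5%. The other arm has:

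- d = 0: 7.5%; risk ratio 1.0.
- d = 0.5: (0.045 + 0.015) / 0.95 = 6.3%; ratio 0.075 / 0.0632 = 1.19.
- d = 1: 0.045 / 0.90 = 5.0%; ratio 0.075 / 0.05 = 1.5, a difference of 2.5 percentage points.

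For the other values of h:

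- h = 0.05: the arm keeping all has 6.25%. At d = 0.5 the other has (0.0475 + 0.0075) / 0.975 = 5.64%, ratio 1.11. At d = 1 the ratio is 0.0625 / 0.05 = 1.25.
- h = 0.20: the arm keeping all has 10%. At d = 0.5 the other has (0.04 + 0.03) / 0.90 = 7.78%, ratio 1.29. At d = 1 the ratio is 0.10 / 0.05 = 2.0.

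**Pairing.** If excluding a tooth removes the child's pair and bleeding is correlated within a child, borderline teeth leave both arms together and the bias shrinks. If a child's two teeth always bleed alike, it is zero.

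**The case against.** The best defence is that this is loose terminology rather than two rules. The timeline row treats the pulpotomy and gaining access as the same thing. Step 10 puts pulp removal and complete haemostasis in one step, and step 11 then allocates. The background definition of pulpotomy in section 6.a also mentions haemostasis. Read together, these make section 16(c) most naturally mean after haemostasis and leave step 3 as the outlier.

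Much of this stands. A reader might infer that the timeline confirms step 3, but it does not: by equating the two terms it fits either text. The section 6.a definition is less help, because it also includes the restoration and so cannot mark a moment before the material is chosen. Step 3 remains an explicit instruction that an operator could follow.

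Three other stronger readings also lack support.

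- A reader might infer that section 16(c) promises concealment up to the last eligibility decision. Its remark about selection bias concerns who performs randomisation and concealment.
- A reader might picture an unsupervised operator. Section 9 says there is no assistant, but section 23 places clinical procedures under the supervisors.
- A reader might take a ratio of 1.5 or 2.0 as the expected bias. Those are the extremes, with every borderline tooth dropped in one arm and none in the other.

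**Conclusion.** The contradiction is real and should be resolved before enrolment. If step 3 is followed, the haemorrhage exclusion is decided with the material known, and selection by arm becomes possible. The documents do not show that it would happen, in which direction, or how often.

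The illustrative risk ratio, for 10% borderline teeth, runs from 1.0 through about 1.19 to 1.5. It rests wholly on assumed rates, independent teeth and no true difference, and it falls with within-child correlation if whole pairs are dropped.

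One limit applies whichever text is adopted. Section 16(a) has one envelope selected per patient. If that envelope fixes both teeth of the split-mouth pair, opening it for the first tooth reveals the material for the second before the second tooth's own exclusion decision.

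**What to change.** Bring section 11 (steps 3 and 11), the section 13 timeline and section 16(c) to one rule: the envelope is opened only after coronal pulp removal is complete and the haemostasis decision under exclusion 3 has been recorded for that tooth. Adopting the present wording of 16(c) alone would leave the order of opening and decision open.

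Add a field for that decision to the Appendix 1 chart, which has none. Log a tooth excluded at that point as excluded before allocation.

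State whether one envelope fixes both teeth. If it does, log haemorrhage exclusions of the second tooth as post-allocation exclusions and report them by material.

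The haemorrhage criterion and the operative steps are unchanged. The cost is a wording change in four places, a statement on the envelope unit, one chart field and a short exclusion log. No visits, staff or procedures are added; the envelope is opened somewhat later in the same visit.

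### Split-mouth is declared, but the allocation text assigns either the person or the tooth and never says which tooth the one-material slip governs or that the other tooth gets the other material

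*Protocol*

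**What the plan says.** The protocol's section 11 (Interventions) says the operator will work "using the split mouth technique, meaning that both groups (I & II) will be in the same patient". Section 10 is consistent with this and requires "Bilaterally Carious vital primary molars with reversible pulpitis". Section 15 likewise recruits children with lesions on both sides. Section 8 (Trial design) says only that the trial is randomised and controlled.

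The allocation text uses other units:

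- Section 11, step 11: "Children will then be allocated into either one of the groups alternatively depending on the pulpotomy medicament used as follows".
- Section 13, timeline: "Allocation of the patient to one of the treatments groups (open the closed white envelope".
- Section 16a: teeth are "randomly assigned one of the experimental groups using closed white envelopes (simple randomization 1:1 ratio".
- Section 16, sequence generation: "By shuffling the envelopes then selecting envelop for each patient upon their enrolment".
- Section 16, concealment: "Using 8-time folded paper on which dressing material was written contained in the closed white envelope". Section 11, step 3 describes the same content.

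A further timeline row reads "Application of pulp dressing material (collagen and Biodentine". It may mean that each child gets both materials, or it may simply list the two arms.

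The moment of opening is given in three ways: once access has been gained (step 3), after the pulpotomy (16c), and, by the order of steps 10 and 11, after haemostasis. Section 10 excludes a tooth in which bleeding cannot be controlled after the pulpotomy.

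**The concern.** In a split-mouth trial, pairing each material with a tooth within the child is the randomisation. Here that step is not written down. A slip that carries only the name of a material randomises nothing in a child with two eligible teeth until a tooth has been fixed for it.

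Three things are at stake. First, a clinic that followed step 11 or the timeline as written would run a parallel-group trial by child and lose the within-child comparison. Second, if the slip's tooth were settled only after reading it, the operator's view of each tooth's prognosis could enter the assignment. The operator is not among those whom section 17 lists as blinded. Third, if the envelope is opened before haemorrhage control is judged, a tooth can be excluded with its material known.

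None of this can be left to an analysis plan. These are chairside instructions, and an assignment that was never fixed or recorded cannot be recovered later.

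**Working it through.** The protocol gives no sample size, success rates or within-child correlation, so there is no stated figure to reproduce. The check sets the allocation rules side by side and asks what each yields.

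**Share of children receiving both materials**, with two study teeth per child:

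| Rule followed | Unit | Children with both materials |
|---|---|---|
| Section 11 declaration | Tooth within child | 100% |
| Step 11 or timeline, literally | Child | 0% |
| 16a alone, two independent 1:1 draws | Tooth | 2 × 0.5 × 0.5 = 50% |
| One slip for one tooth, the other tooth gets the other material (nowhere stated) | Tooth within child | 100% |

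The third row is a limit case, because section 16 describes one draw per patient. Only the fourth rule turns a single one-material slip into the declared design, and it is the one that is not written.

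**Tooth-choice bias.** Suppose the materials are equivalent, the two teeth of a child differ in success probability by *d* points, and collagen goes to the better tooth with probability *q*. The expected difference is *qd* − (1 − *q*)*d* = (2*q* − 1)*d*.

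- Tooth fixed before a random slip is opened: *q* = 0.5, bias 0 whatever *d* is.
- Tooth chosen after opening, assumed *d* = 10: *q* = 0.6, 0.75, 1.0 gives 2, 5, 10 points.
- The same with assumed *d* = 5: 1, 2.5, 5 points.

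**Precision.** Take *N* children, two treated teeth each, per-tooth variance *s*² and within-child correlation *r*.

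- Split-mouth: 2*s*²(1 − *r*)/*N*.
- Whole-child allocation: 2*s*²(1 + *r*)/*N*. The ratio to split-mouth is (1 + *r*)/(1 − *r*) = 1.22, 1.86, 3.00 for assumed *r* = 0.1, 0.3, 0.5.
- Independent teeth, unweighted: 2*s*²/*N*. The ratio is 1/(1 − *r*) = 1.11, 1.43, 2.00.
- Independent teeth, precision-weighted: the discordant half gives 4*s*²(1 − *r*)/*N* and the concordant half 4*s*²(1 + *r*)/*N*. Combined, this is 2*s*²(1 − *r*²)/*N*. The ratio is 1 + *r* = 1.10, 1.30, 1.50.

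These are alternatives, one per reading, and do not add up. The values of *r*, *d* and *q* are assumptions.

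**Opening time.** Under 16c, or the order of steps 10 and 11, the pulpotomy comes before opening. Only the order of the steps places haemostasis before opening as well. Under step 3 read literally, opening comes before the pulpotomy is complete, and so before the haemorrhage exclusion can be judged.

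**The case against.** The strongest reply is that the intention is plain. Section 11 does not merely mention split-mouth but defines it, bilateral lesions are required, and one operator treats every tooth. The order of steps also supplies a tie between slip and tooth: step 9 anaesthetises the side of a single tooth, step 10 carries out the pulpotomy, and the envelope is then opened to settle the material. Read so, the slip belongs to the tooth just opened. That tooth was chosen while the slip was sealed, so *q* = 0.5 and the bias is zero.

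Much of this stands. A reader might infer from the missing tooth rule that allocation is biased by the operator. The documents do not support that: a non-zero bias needs both teeth opened before the slip is read, or the slip moved to an unopened tooth, and neither is described. Nor do they show that the trial will in fact run as a parallel-group study. The 0% and 50% figures and the variance ratios measure literal readings that were probably not intended.

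The reply does not remove the contradiction. The tie has to be inferred from the order of the steps, nothing requires the first tooth to be recorded, and no sentence gives the contralateral tooth the other material.

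On opening time, the timeline describes the pulpotomy as gaining access to the pulp, so step 3 and 16c may mean the same moment. Exclusion that depends on the material is therefore possible, not shown.

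Two further inferences should be resisted. The adverb in step 11 can be read as alternation between children, but may only mean one or the other, and section 16 describes shuffled envelopes. Appendix 1 has one field for material and one for tooth, but a chart could be completed for each tooth.

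**Conclusion.** The point holds as a contradiction within the protocol: the declared design is within-child, while the allocation rules name the child, the patient and the tooth as units. The sentence that would make one envelope deliver the design is absent. Followed as written, person-level allocation gives 0% of children both materials, and 16a taken alone about 50% as a limit case, against 100% under the declared design.

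On the probable intended reading the assignment is unbiased, provided that the tooth was fixed before opening. The protocol neither states nor records this. The opening time must also be reconciled, because step 3 read literally allows the haemorrhage exclusion to be judged with the material known. The bias and variance figures are illustrations under assumed *r*, *d* and *q*, not properties of this trial.

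**What to change.** State one mechanism, for example: one sealed opaque envelope is drawn per child; its slip randomly assigns material to side, either right collagen and left Biodentine or the reverse, in a 1:1 ratio; the two study teeth within a child are the units compared.

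- Before the envelope is opened, identify and record the one study molar on each side (a side may have more than one eligible molar) and which is treated first.
- Align six places: step 3 (envelope content and opening time), step 11 (drop the child-level wording and its adverb), the timeline allocation row, 16a, 16b and 16c. Simple 1:1 can stay if it refers to the side assignment.
- Use a single opening time, after the haemorrhage exclusion has been judged in the first tooth. The second tooth's material is then unavoidably known, so report second-tooth exclusions by assigned material.
- Give Appendix 1 separate tooth, material and follow-up entries for each tooth.

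The cost is wording in about six places, reprinted slips and a revised chart. No extra staff, visits or patients are needed.
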